1.9 Brainstem reflex

Trigeminal blink reflex, mediated by trigemino-facial ponto-medullary-circuits will be assessed. Surface recording electrodes will be attached over the *orbicularis oculi* in both sides with active electrode over the middle part of the lower eyelid and the reference at the lateral canthus of the eye. Stimulating electrodes will be placed over the supraorbital nerve. Ipsilateral (R1, R2) and contralateral responses (R2c) latencies measured in ms will be analyzed.

2) Development an animal model of anti-LGI1 encephalitis using active immunization

2.1. Behavioral studies. From baseline (pre-immunization) until day 71 (euthanized) animals will be regularly tested with an extensive panel of memory/behavioral paradigms, as reported in our model of passive transfer of antibodies (*Petit-Pedrol et al., Brain 2018;141:3144-59*).

2.2. Effects on LGI1. The antibody effects will be determined in subsets of mice euthanized at day 42 (acute phase) and the rest of mice on day 71 (chronic phase). Sections of cortex/hippocampus will be examined using (1) confocal microscopy and IMARIS software to quantify the total surface and synaptic clusters of LGI1 and their synaptic protein partners (Kv1.1 and AMPA receptor), and (2) electrophysiology to assess hippocampal long-term (LTP) and short-term potentiation (STP). These techniques were described in detail in our passive immunization models of NMDAR and LGI1 antibodies (*Planagumà et al., Brain* 2015;138:94-109; *Petit-Pedrol et al., Brain* 2018;141:3144-59).

2.3. Immune cells and immune-inflammatory pathways. From tissue samples obtained on days 42 and 71, immune/ inflammatory cells (B, T, activated microglia, etc.) will be examined by immunohistochemistry with antibodies specific for the indicated cell types, as reported (Planagumà et al., *Brain* 2015;138:94-109). RNA will be extracted from brain for RNA/NanoString analysis targeting the same genes as described in patients (see Annex Table), with mice-RNA primers. Findings from the acute stage (day 42) will be compared with the post-acute stage (day 71).

5 Design of the study

Human studies

Clinically characterization of the post-acute stage of anti-LGI1 encephalitis: Prospective single center, single arm, national study of 3 years duration.

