Human studies: Cross-sectional comparisons among the 2 groups of patients will be done with Analysis of Covariance (ANCOVA) and Chi-Squared tests, as appropriate. Post-hoc analyses with Bonferroni correction for post-hoc multiple comparisons will be applied to all analyses. Analysis of inter- and intragroup differences in the longitudinal follow-up will be done using multilevel linear mixed-effect (LME). Lme4 R package (version 1.1-27.1) will be used to fit LME models. Comparisons will be done with emmeans library (version 1.7.3) and Tukey method for post-hoc correction for multiple testing. The global tendency of recovery of cognitive deficits in patients receiving or not cognitive training will be assessed with the Cochran-Armitage test for trend. All analyses will be addressed considering a two-tailed type I error of 5% with statistical

significance set at p-value <0.05, using SPSS (version 25; IBM Corp, Armonk, NY) and R package (version 4.1.2; Vienna), as previously reported (*Guasp et al., Lancet Neurol 2022;21:899-910*).

Animal studies: Animal behavior with multiple determinations in time (e.g., recognition of new object) will be analyzed using repeated measures two-way analysis of variance (ANOVA). Behavioral studies with a single time determination (e.g., depressive behavior) will be analyzed with one-way ANOVA or Mann-Whitney-U for skewed distributions (e.g., tail suspension). The intensity of IgG deposits in brain and electrophysiological studies (long-term potentiation) will be analyzed with two-way ANOVA. The reactivity intensity of the antibodies of patients in HEK cells (CBA), neuron cultures, or brain tissue, or quantification of synaptic markers (e.g., GluN1, PSD95) or activated microglia, in a single time determination, will be analyzed by one-way ANOVA. Post-hoc analyses for all experiments will use Bonferroni correction for multiple testing. A p value of <0.05 will be considered significant and the α -error will be set to 0.05. Analyses will be done with GraphPad Prism v7 (*Planagumà et al., Ann Neurol 2016;80:388*).

9. Risks and benefits for participants in the study

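### For mouse tissue from two sacrifice days, Section 8 names a one-way ANOVA with no group-by-day term, and it does not fix the mouse as the unit for sections, clusters and slices

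*Protocol*

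**What the plan says.** **Methods named (Section 8, Animal studies).**
- Behaviour measured several times "will be analyzed using repeated measures two-way analysis of variance (ANOVA").
- For IgG deposits and long-term potentiation: "The intensity of IgG deposits in brain and electrophysiological studies (long-term potentiation) will be analyzed with two-way ANOVA". The two factors are not named.
- For quantified synaptic markers "or activated microglia, in a single time determination, will be analyzed by one-way ANOVA".
- Error level: "A p value of <0.05 will be considered significant and the α -error will be set to 0.05". Post-hoc comparisons get a Bonferroni correction.

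**Design these methods serve.**
- Section 4.1, item 2.2, on timing: "The antibody effects will be determined in subsets of mice euthanized at day 42 (acute phase) and the rest of mice on day 71 (chronic").
- Item 2.2, on what is measured: "Sections of cortex/hippocampus will be examined using (1) confocal microscopy and IMARIS software to quantify the total surface and synaptic clusters of LGI1", together with its synaptic partners. Hippocampal potentiation is also recorded.
- Item 2.3, on immune cells (including activated microglia) and RNA: "Findings from the acute stage (day 42) will be compared with the post-acute stage (day 71").
- Section 5 adds a control group given adjuvant and toxin without peptide, mentions acute brain slices, and gives 104 mice in total with no breakdown.
- Section 3, hypothesis 3, postulates long-lasting alterations that reproduce the chronic as well as the acute phase.

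**The concern.** There are two separate issues.

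**Model against design.** The natural layout is two groups by two sacrifice days. For synaptic markers and microglia, Section 8 names a one-factor model meant for a single time. Such a model can compare the groups on one day, or the days within one group, but it has no term for a change in the peptide effect between days. Two substitutes are then tempting, and both are weak. Comparing immunised mice on day 42 with immunised mice on day 71 mixes the peptide effect with anything that also changes in controls, such as a fading response to the adjuvant. Finding significance on one day and not on the other is not a test of the difference. Duration is what hypothesis 3 holds up against the older passive-transfer model, so this matters for Objective 3.

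**Unit of analysis.** Several sections, clusters or slices can come from one mouse, and readings within a mouse are usually correlated. Section 8 handles within-subject correlation for repeated behaviour (repeated-measures ANOVA) and for patients (mixed models), but for tissue and slices it names plain ANOVA. Entering every reading as an independent value would comply with the text, and the false-positive rate could then exceed the stated 0.05. The Bonferroni correction does not repair this, because it adjusts for the number of comparisons and not for correlated readings.

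**Working it through.** **1. What can be reproduced.** The only figures given for the animal work are the 104 mice and the 0.05 level. Group size, effect size, standard deviation and readings per mouse are not stated, so 104 cannot be re-derived.

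**2. What each model tests.** Write P and C for the peptide and control means.
- Presence on day 71: P71 − C71. A one-way ANOVA of the two groups on day 71 tests this.
- Change between phases: (P71 − C71) − (P42 − C42). This is the group-by-day interaction. A one-way ANOVA on a single day does not contain it.

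Section 8 therefore supports the first question for synaptic markers and microglia and names no test for the second. Item 2.3 announces the day comparison for immune cells, hence for microglia. For synaptic markers the protocol collects tissue on both days, and hypothesis 3 covers them.

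**3. Error rate if readings are pooled.** Inputs, all assumed because the protocol gives none: m readings per mouse, within-mouse correlation ICC, 8 mice per group.

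Design effect: DE = 1 + (m − 1) × ICC. Approximate true two-sided level: 2 × [1 − Φ(1.96 / √DE)].

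| m | ICC | DE | 1.96/√DE | Formula | Simulation |
|---|---|---|---|---|---|
| 3 | 0.2 | 1.4 | 1.66 | 10% | 9.7% |
| 3 | 0.5 | 2.0 | 1.39 | 17% | 17.6% |
| 10 | 0.2 | 2.8 | 1.17 | 24% | 24.5% |
| 10 | 0.5 | 5.5 | 0.84 | 40% | 41.5% |

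The simulations used 20,000 runs, two groups and no true effect, with a two-group test on pooled readings. A second set over a wider range (ICC 0.05 to 0.5; 5, 8 or 10 mice per group) gave 6–18% for m = 3, 7–28% for m = 5, 10–43% for m = 10 and 16–56% for m = 20.

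**4. The same check for the interaction.** With 8 mice in each of four cells and ICC 0.3, pooled readings gave 19% (m = 5) and 31% (m = 10).

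**5. One value per mouse.** Tests on mouse means gave 4.6–5.4% in every two-group scenario and 4.7–5.1% for the interaction. The named ANOVAs are valid at that level.

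**The case against.** The strongest reply is that the protocol never makes the section, slice or cluster the unit of analysis. If the laboratory averages within mouse, the named ANOVAs hold their level. The techniques are said to be described in cited papers, and the unit could be stated in an analysis plan that is not at hand. This stands as a limit on the claim. A reader might infer that Section 8 inflates false positives, but the document supports only that it leaves this open.

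A reader might also infer that persistence goes untested. It does not:
- A one-way comparison of peptide and control mice on day 71 tests presence in the chronic phase.
- A one-way ANOVA over four group-by-day cells with a chosen contrast could even recover the interaction, although none is specified.
- The unnamed factors of the two-way ANOVA for IgG deposits and potentiation may already be group and day.
- Behaviour is followed to day 71, with repeated-measures ANOVA for tests given several times.

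Nor do the two sacrifice days create clustering. Different mice are killed on each day, so correlation can come only from several readings within a mouse.

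Finally, these are endpoints of the animal objective, and no patient comparison depends on them. That limits the weight of the point but does not remove it. The one-way ANOVA is what the protocol states, and it does not fit the two-day collection and comparison that Section 4.1 also states.

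**Conclusion.** The point holds in a limited form. For synaptic markers and activated microglia, the model named in Section 8 has no group-by-day term, although tissue is taken on days 42 and 71 and hypothesis 3 concerns both phases. Change in the peptide effect between phases has no named test; presence at day 71 can be tested. This reading takes controls to be killed on both days, which the protocol implies but does not spell out.

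The error-rate part is conditional. If several readings per mouse are pooled as independent, the true level is about 10–18% with 3 readings and 24–42% with 10, assuming 8 mice per group and ICC 0.2 to 0.5. With few readings and weak correlation it can be as low as 6%. With one value per mouse it is 5%. The protocol does not say which case applies, so its 0.05 is not secured by its text, but it is not shown to be breached either.

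**What to change.** Amend Section 8, Animal studies:

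1. State that the mouse is the experimental unit for all tissue and slice endpoints. Analyse one mean per mouse, or use a linear mixed model with a random mouse effect. The two agree exactly only when every mouse contributes the same number of readings; with unequal numbers, say which is used.
2. For endpoints collected on both days, replace one-way ANOVA with a model in group, day and group-by-day. Name the two factors of the ANOVA for IgG deposits and potentiation.
3. Name the peptide-versus-control difference at day 71 as the persistence contrast, and the interaction as the test of change between phases.
4. Say that controls are killed on both days, if that is the intention.

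**Cost.** A few sentences and no new measurements. Intervals will be somewhat wider than from pooled readings. The interaction is also less precise than the day-71 difference: with n mice per cell its variance is 4σ²/n against 2σ²/n, so its standard error is √2 ≈ 1.4 times as large. A non-significant interaction should therefore not be read as proof that the effect is unchanged. Whether 104 mice are enough cannot be judged without group sizes.
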